<https://www.hra.nhs.uk/approvals-amendments/managing-your-approval/progress-reports/> will be used. It will be completed and signed by the chief investigator and emailed to the REC within 30 days of the anniversary date of the favourable opinion and annually until the trial is completed.

Data collection, handling, management and record keeping

Data will be collected by the local principal investigator at all time points during the study. Collection of data will be via standardised questionnaires (VascuQoL and SF-36) and physical assessment. To ensure completeness of data, questionnaires will be issued and completed during the study visits to allow patients to ask questions or clarify information about the questionnaire. Data will be collected and retained in accordance with the Data Protection

Act 1998. All patients will be given a study code along with the abbreviate hospital title to ensure anonymity, for example the first patient recruited at Hull and Coventry would be 01H and 01C respectively. Data will be stored on computers in the research office at the vascular laboratory in Hull Royal Infirmary and Coventry and Warwickshire University Hospital respectively with the same identification code. These computers are password protected and have both antivirus and firewall software. Only named investigators will have access to the patient data. Transfer of electronic data will be anonymous and only be carried out through encrypted password protected USB devices or via the secure www.nhs.net email account. Data will be stored for five years following trial completion.

IT services department has a backup procedure approved by auditors for disaster recovery. Servers are backed up to disk media each night which run on a 4-week cycle, meaning anything deleted more than 4 weeks previously is lost. Files remain on the server unless deleted either accidentally or deliberately. Additional 'archive' backups are taken for archived data, so data should not be lost from this system e.g. FileVision. Disks are stored in a fireproof safe.

Study documents (paper and electronic) will be retained in a secure location during and after the trial has finished. All essential documents including source data will be retained for a minimum period of 5 years after study completion. A sticker stating the date that documents need to be retained until will be placed on the inside front cover of participant case report forms.

Direct access will also be granted to authorised representatives from the sponsor, host institution and the regulatory authorities to permit trial-related monitoring, audits and inspections – in line with participant consent.

Project Management Group;

The overall management of this study will be the responsibility of the Programme Management Group. This will be chaired by the R&D Director, HEYHT, who is independent of the research team. Membership of the Project Management Group will comprise all coapplicants, patient representatives and [name] (Finance Manager). The Trust will discharge its sponsorship responsibilities through this Group including research governance and financial oversight and will ensure that the research conducted is congruent with that specified in the proposal and of value to the NHS. Additionally this group will provide specialist advice in areas of data collection, analysis and interpretation, consider the implications of the findings, develop a dissemination strategy, and consider any issues brought to their attention by the research staff. The Project Management Group will meet on a quarterly basis and receive reports from, and oversee, the work of the Project Delivery Group.

Combined Trial Steering / Data Monitoring Committee; will be formed to monitor the progress of the study, provide independent advice, and monitor the data arising from the study to recommend whether there are any ethical or safety reasons why the study should not continue. This committee will comprise independent clinicians and health service

researchers with appropriate expertise, a patient representative and will also be attended by the trial statistician. This committee will meet every 6 months to provide oversight to the study.

Source data

It is important that information from a patient study visit is recorded clearly into the casenotes so that other clinicians and healthcare professionals can be aware of any relevant results or information which may affect ongoing care.

The minimum information recorded in patient notes following each study visit or phone call will be:

- Clearly written date of visit, study short title and visit number.
- The date that the patient information sheet was given
- The date informed consent was obtained
- Medical history (including reasons for referral), concomitant diseases, and medications and any changes between visits. Any changes or newly developed symptoms or are they asymptomatic.
- Anything relevant to the ongoing care of the subject
- Relevant investigations and results of these – i.e. ABPI, CPET (any ECG changes)
- Brief description of any AE's with start and end dates if appropriate, any significant tests/results or a medical summary of events.
- Any other relevant information.

Protocol deviations/serious breaches

Protocol deviations and serious breaches will be acted upon in line with the HRA standard operating procedure version 7.2 available from <https://www.hra.nhs.uk/about-us/committees-and-services/res-and-recs/research-ethics-committee-standard-operating-procedures/>.

Protocol deviations involves not complying with the protocol as a result of fraud or misconduct. Accidental protocol deviations must be adequately documented and reported to the CI and sponsor immediately. However, the sponsor does not need to notify the REC unless the deviation constitutes a serious breach. Any deviations will also be documented in the patients notes and with a file note in the site, detailing as much information as possible.

Importantly, frequent and/or recurrent deviations are not acceptable and will require immediate action and could lead to a serious breach.

A serious breach is defined as a breach of the protocol, conditions or principles of GCP which is likely to affect to a significant degree the safety or physical or mental integrity of the trial subjects or the scientific value of the research. Serious breaches will be reported to the sponsor immediately upon knowledge of the breach. The PI will take a leading role in resolving any serious breach whilst completing any additional activities required by the sponsor to investigate or address the breach.

The sponsor should also notify the REC of a serious breach within 7 days of being informed. A report of the serious breach which should outline when and where it occurred, who was involved, the outcome and any information given to the participant should be provided by the CI or other representative of the sponsor, and copied to the sponsor. The REC should receive an explanation and informed of any further action that the sponsor plans to take.

End of trial

The trial will be complete once the last patient has attended their final follow-up visit, for this study, the last study visit will be 12-weeks post-intervention.

The REC which gave the favourable opinion will be notified of the study conclusion by the CI within 90 days or within 15 days if the trial is terminated early (with reasons). This notification will be in writing (sent via email) using the appropriate form available from: <https://www.hra.nhs.uk/approvals-amendments/managing-your-approval/ending-your-project/>

A final research report summary will be emailed by the CI to the REC within 12 months of the end of the trial. The summary will include information about whether the research achieved its objectives, the main findings and arrangements for publication, including any patient feedback.

Quality control and assurance:

Peer review

This study has been peer reviewed by:

[name], Postdoctoral research fellow, academic vascular surgical unit, Hull Royal Infirmary.

[name], consultant vascular surgeon, Hull Royal Infirmary.

[name], consultant vascular surgeon, Hull Royal Infirmary.

[name], Reader in Trials and member of the Senior Management at the York Trial Unit. [name] is also the lead for the North and East Yorkshire spoke of the Research Design Service Yorkshire and Humber (RDS-YH). This application has been developed in

collaboration with our PPI members of the “Humberside Peripheral Arterial Research Involvement Group

Monitoring

Research will be monitored in accordance with GCP. The sponsor has the responsibility to ensure that the rights and safety of participants are protected, study data is complete and accurate and that conduct of the study complies with the protocol and GCP. Monitoring will be risk based as required by the sponsor.

Ethical considerations

REC review and reports:

Before trial commencement, approval will be sought from the REC for the trial protocol, informed consent forms and other relevant documents such as GP letters and patient information sheets.

Substantial amendments requiring review from the REC will not be implemented until the REC grants a favourable opinion. All correspondence with the REC will be retained in the trial master file.

Indemnity

This is an NHS-sponsored research study. If there is negligent harm during the clinical trial when the NHS body owes a duty of care to the person harmed, NHS indemnity covers NHS staff and medical academic staff with honorary contracts only when the trial has been approved by the Trust R&D department. NHS indemnity does not offer no-fault compensation and is unable to agree in advance to pay compensation for non-negligent harm. Where the Chief/Principal investigator is employed by the University of Hull, the University has an insurance policy that includes cover for no-fault compensation in respect of accidental injury to a research subject.

Amendments

Amendments involve changes to a project after initial approval has been granted. It is the responsibility of the sponsor to decide whether an amendment is substantial or non-substantial. If the sponsor deems an amendment to be non-substantial the template available from <https://www.hra.nhs.uk/approvals-amendments/amending-approval/> will be emailed to [contact]. The amendment will receive two possible outcomes; ‘HRA approval for the amendment confirmed’ or ‘HRA approval for the amendment pending’.

The applicant will communicate this outcome, along with the amendment application, with the site team, R&D office and local CRN. For category A and B amendments, the site team have 35 days to raise any objections, after which if no objections are raised, the amendment

can be implemented. Category C amendments can be immediately implemented. Where HRA approval is required, the amendment will be reviewed and approval issued. The applicant should then notify the site team and provide the approved documentation.

A similar process is followed for substantial amendments. The notice of substantial amendment form in IRAS will be used to generate a PDF form for the amendment that will be emailed to the REC that gave the favourable opinion of the original study. The REC staff will validate the amendment and if necessary, categorise it. The applicant will then receive a validation letter which will also outline the categorisation – which should be passed onto site staff. The REC will then review the amendment, with three possible outcomes; an unfavourable opinion, which will require restarting the process and resubmitting, or a favourable opinion either with or without further review from the HRA. If either of the favourable opinion outcomes is given, the same outcome communication and implementation process as described above for a non-substantial amendment will be followed.

An amendment history table will also be used to identify the most recent protocol version (appendix 1).

Reporting and dissemination

The final trial dataset will be developed by the principal investigators but will be owned by the Academic Vascular Surgical Unit and as such can be accessed by site investigators. Upon completion of the trial, data will be analysed and tabulated with a final trial report prepared and submitted to the REC. The study will also be reported in peer-reviewed scientific journals, an internal report and conference presentation. Patients will be offered individual information regarding post-intervention improvements and access to publications should they request it.

Finance and conflicts of interest

Patients will not be paid for participating in the trial, but will be offered a discounted parking permit of £20 per month if required for the intervention period.

There are no ownership or commercial ties related to any of the interventions. The principal investigator in Hull is funded by a University of Hull scholarship.

Study equipment

Height measure – Leicester height scale, Seca LTD. UK

Weight scales – Marsden, Charder M-420, UK

Resting Blood Pressure monitor – Welch Allyn, Sure Temp. technology, UK

Ambulatory blood pressure monitor –

12-lead ECG – Mortara Instruments, T2, USA

ECG electrodes – 3M Red dot, Canada

Cycle ergometer – Lode Corival, Neterlands

CPET system and metabolic cart – MedGraphics Ultima series with BreezeSuite software

Doppler – Ultrasonic Doppler flow detector, LifeDop, Summit Doppler, Wallach, USA.

Wattbike – Wattbike Ltd. Nottingham, UK.

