Those who decide to participate will be asked to attend a baseline visit prior to beginning their exercise programme to determine if they are suitable. The research project will be re-explained and questions encouraged. Following this, informed consent will be obtained if appropriate. A clause outlining the conduction of an interview, voice recording and use of anonymous quotes will be included in the consent form, but this will be optional. Patients will still be able to participate in the study without completing an interview.

Baseline and follow-up visits

Baseline and follow-up visits will be completed for all research participants who complete the full intervention timeframe (i.e. 6-8 weeks). Those choosing to discontinue the intervention before completing the full intervention timeframe will be withdrawn. Follow-up visits will be completed immediately following completion of the HIIT programme, and then 12-weeks post-intervention. An additional follow-up will also be completed 4-weeks post-intervention at the Hull site only.

[figure not shown]
Travel expenses for study visits (baseline and follow-ups) will be reimbursed. Patients can be reimbursed a maximum of £75 to cover the costs of transport/parking that may be accrued.

Patients will be asked not to eat a heavy meal or smoke for 3 hours before the visit and testing (18). Patients will also be asked to dress appropriately, especially in terms of footwear and instructed to avoid unusual physical activity efforts in the preceding 12 hours (18). As testing will not be performed for diagnostic purposes, patients will not be asked to withdraw or refrain from taking any medications (18). At each study visit, the patient's medical notes will be reviewed before assessment of current and past medical history. Patients will be asked questions relating to previous medical history including previous

diagnoses, current symptoms, and medications to determine the presence of any contraindications to exercise testing (18, 19).

Resting blood pressure and HR will then be taken followed by height, weight, body mass index (BMI), waist circumference, hip circumference and waist to hip ratio. During the baseline and subsequent visits, a number of objective physiological and subjective patient-level measures will be performed.

Trial Procedures

Measurement of primary and secondary endpoints

Primary endpoint – safety, utility and tolerability

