Safety will be determined by the occurrence of any adverse events (AE) or serious adverse events (SAE). In accordance with the GCP decision tree for adverse event reporting all events will be reported to the sponsor and recorded to determine the safety of the intervention.

Utility will include eligibility (n = eligible/screened), recruitment (recruited/eligible), and adherence (number of patients completing the HIIT programme). The number of patients screened, recruited and commencing the HIIT programmes will be monitored at each hospital site. A register (if required, i.e. more than one patient attending), will be taken at each exercise class to record patient adherence and the completeness of each session will be recorded (i.e. how many minutes the patient completed). It is estimated that all patients should complete 18 sessions in total within 6 weeks. However, where any sessions are missed, the intervention period can be extended to 8 weeks to allow these sessions to be added on. Those not completing 18 sessions over the extended 8-week period will be deemed to have satisfactorily completed the intervention as long as they have completed >80% of the intervention (i.e. ≥ 15 out of 18 sessions). All patients completing the allotted 6-8 weeks for the intervention (regardless of whether they have completed \geq or < 15 sessions) will still be followed up. Those choosing to discontinue the intervention before completing the full intervention timeframe will be withdrawn.

Tolerability will be assessed by identifying if patients are able to reach and maintain the prescribed training range required to perform HIIT, for each full interval. Heart rate (HR) data will be collected throughout each HIIT session and saved on an encrypted USB stick this will then be compared to the 85-100%HRMax training range that has been prescribed – to determine if patients are able to achieve it. This range will be in line with an ongoing HIIT trial in CAD at 85-90% peak power output (PPO), aiming to achieve >85%HRMax, derived from CPET (15). If patients are not able to achieve 85-100%, this will determine the suitability of this HIIT protocol in this population. Reasons for stopping the HIIT exercise sessions (e.g. leg pain), will be recorded.

Secondary endpoints

Acceptability

Acceptability will be assessed by patient feedback using semi-structured interviews.

conducted using a sample of patients in three groups:

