The HIIT intervention will be performed by using a cycle ergometer with exercise prescription based on the workload achieved during a cycle CPET. The use of a treadmill may preclude patients from reaching their prescribed HIIT training zones due to the onset of claudication whilst a cycle may reduce the risk of falls in very deconditioned patients (34). It has been demonstrated that the limiting symptoms during treadmill walking were often experienced in the leg, mainly the calf, whereas the limiting symptoms during cycling were much more varied (34). Furthermore, one study, albeit small, noted that cycle testing was better tolerated than treadmill testing, which is important considering that the HIIT training zone requires the patient to exercise to near-maximal levels, similar to during a CPET (35).

Inclusion criteria:

- Community dwelling adults aged 18 or over.
- ABPI <0.9 at rest or a drop of more than 20mmHg after exercise testing
- Ability to walk unaided
- English speaking and able to comply with exercise instructions

Exclusion criteria:

- Patients who are unable to provide informed consent
- Critical limb ischaemia/rest pain
- Active cancer treatment
- Significant comorbidities precluding participation in exercise testing and/or training as per the American College of Sports Medicine Guidelines (19).
- Resting/uncontrolled tachycardia (>100bpm) and/or Resting/uncontrolled hypertension (SBP >180mmHg or DBP >100mmHg)
- Symptomatic hypotension

Additional exclusion criteria

Further to analysis of CPET results, patients will be prevented from continuing their involvement in the study if there is indication of:

- Exercise-induced ischaemia or significant haemodynamic compromise.

N.B. – Patients who are able to perform a maximal effort CPET according to previously published guidelines (19) will undergo the intervention which will be prescribed on the basis of their initial CPET. This will be referred to as maximal HIIT.

Patients unable to perform a maximal effort CPET, will still undergo the intervention which will be prescribed on the basis of their initial CPET values, but will be referred to as submaximal HIIT.

Subject recruitment

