Patients who are deemed appropriate for referral to SEP as is usual practice will be informed of the research study evaluating HIIT as a novel exercise intervention for IC. Patients will then be sent a patient information sheet, detailing the aims and details of the study and what the intervention entails. Patients will then be contacted via telephone at least a week later to discuss their interest to undertake the intervention. Those who choose to participate in the study will be asked to attend for baseline assessment. Those who do not choose to partake in the research will be offered the usual SEP, without research. Those also declining the usual SEP will be referred back to their consultant.

Withdrawal of subjects

Participants are free to withdraw at any time and do not have to give a reason for doing so. If a participant exhibits any of the exclusion criteria or loses capacity to consent after enrolment on the study, they will be withdrawn. Full details of any withdrawal will be recorded in the case report form and withdrawal can occur at any time, including during the intervention or follow-up.

Trial exit

Patients will exit the trial if:

- They have completed their intervention and all follow-up assessments.
- They request or are unable to continue intervention or follow-up
- They suffer an adverse or serious adverse event meaning they are no longer able to continue
- They lose the capacity to consent
- They die.

General information**Potential patient benefits**

SEPs have proven to be effective for improving walking distance in patients with IC but are not always feasible or available (11, 14, 36). Other exercise interventions may provide a similar benefit and allow access for a greater number of patients. HIIT has demonstrated beneficial effects in the cardiac population (33, 37), which may be transferrable to the IC population, due to the similar disease aetiology. Therefore, patients may benefit from having a greater range of exercise options that may provide similar benefits, allowing them

to choose their preferred option, thus increasing availability and potentially uptake and adherence.

Potential risks/barriers to the patient

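### The secondary efficacy changes will describe only patients who stayed in HIIT for the full 6-8 weeks; the plan does not label them so and does not test what the losses do

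*Combined protocol and SAP*

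**What the plan says.** **Who is followed.** Under Baseline and follow-up visits: "Baseline and follow-up visits will be completed for all research participants who complete the full intervention timeframe (i.e. 6-8 weeks". Post-baseline visits take place straight after the programme and 12 weeks later, with an extra 4-week visit at Hull only. That section and the one on the primary endpoint (safety, utility and tolerability) both state: "Those choosing to discontinue the intervention before completing the full intervention timeframe will be withdrawn".

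**Length of the programme.** "It is estimated that all patients should complete 18 sessions in total within 6 weeks", and if sessions are missed, "the intervention period can be extended to 8 weeks to allow these sessions to be added on". Fifteen of 18 sessions counts as satisfactory. Patients who remain for the period are followed up however few sessions they attended.

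**Leaving the trial.** One reason listed under Trial exit is "They request or are unable to continue intervention or follow-up". Another entry covers an adverse event that prevents the patient from continuing.

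**Analysis.** Descriptive statistics and statistical analysis includes all participants, excludes nobody for poor adherence, and then narrows this to whatever data were collected at each time point. Changes in MWD, PFWD, VO2Peak, VAT, ABPI and QoL are tested with a repeated-measures general linear model in SPSS. Missing data are not imputed. Dropout and missing outcome data are summarised. The sub-group comparison by session count assumes that patients have not withdrawn.

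**Safety.** For adverse events, "all events will be reported to the sponsor and recorded to determine the safety of the intervention"; for withdrawals, "Full details of any withdrawal will be recorded in the case report form". Patients are asked about their health at each study visit, and AE reporting ends 30 days after the final visit.

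**The concern.** Efficacy is part of the Work-stream 1 objective, and its results will carry p values and confidence intervals. A reader who sees that all participants are analysed would take the changes to apply to everyone who began HIIT. Yet every efficacy measurement after baseline falls after the programme, so a patient who stops early has a baseline value and nothing to compare it with.

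Stopping may also be related to the outcome. The protocol gives leg pain as an example reason for stopping a session, and it acknowledges that attending three times a week may lead some recruits to withdraw. Its retention measures (early contact, rearranged appointments) do not reach patients already withdrawn by rule. With no control arm, no imputation and no sensitivity analysis, the report could not show whether the stayers' change resembles that of all starters.

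**Working it through.** **1. The plan's own figures.** Sites: 50 + 20 = 70. Sessions: 3 per week × 6 weeks = 18. Threshold: 15/18 = 83.3%, and 14/18 = 77.8%, so 15 is the smallest count above 80%. All agree with the text.

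**2. What each kind of patient contributes.**

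| Patient | Baseline | Later efficacy data | Why |
|---|---|---|---|
| Stays 6-8 weeks, 15 or more sessions | yes | yes | followed up |
| Stays 6-8 weeks, few sessions | yes | yes | followed up regardless of count |
| Chooses to stop earlier | yes | no | withdrawn |
| Unable to continue, including after an AE | yes | no | trial exit |

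The rule depends on time, not on sessions. At 3 sessions per week, 15 are reached at the end of week 5 (3 × 5). A patient who then chooses to stop is not measured, while a patient with far fewer sessions who stays on is.

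**3. Possible size.** Let w be the proportion of starters who stop early, and k the stoppers' mean change divided by the stayers'. Setting the stayers' mean to 1:

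all-starters' mean = (1 - w) + wk, so stayers' mean / all-starters' mean = 1 / (1 - w(1 - k)).

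The documents give neither w nor k, so both are assumed:

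| k | w = 10% | 20% | 30% | 40% |
|---|---|---|---|---|
| -0.5 | 1.18 | 1.43 | 1.82 | 2.50 |
| 0 | 1.11 | 1.25 | 1.43 | 1.67 |
| 0.5 | 1.05 | 1.11 | 1.18 | 1.25 |
| 1 | 1.00 | 1.00 | 1.00 | 1.00 |
| 1.5 | 0.95 | 0.91 | 0.87 | 0.83 |

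Example: w = 0.2 and k = 0 give 1/(1 - 0.2) = 1.25.

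**4. Patients without later outcomes.** If all 70 start, 70w = 7, 14, 21 or 28. This is an upper limit, because after the baseline CPET "patients will be prevented from continuing their involvement in the study if there is indication of" ischaemia or haemodynamic compromise. If 10% were removed at that step (assumed), 63 would start and 63w is about 6, 13, 19 or 25. The ratios do not depend on the number of starters.

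**5. The model.** The plan does not say how the general linear model treats a missing visit. Under listwise deletion, the usual SPSS behaviour, anyone missing a modelled visit is dropped. If the Hull-only 4-week visit is in the model, all Coventry patients go and at most 50 of 70 remain.

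**The case against.** The strongest reply is that the plan is open about whom it follows and that little hangs on these outcomes. This is a single-arm proof-of-concept cohort without a sample-size calculation. The primary endpoints are utility, safety and tolerability, and adherence already counts stoppers as non-completers. Minutes completed, reasons for stopping sessions and dropout rates are recorded, and patients who drop out may be interviewed. All of this stands, and it limits the weight of the point. It does not supply an outcome for stoppers or say whom the efficacy changes describe.

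Some stronger readings are tempting but not supported:

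- **That the analysis section contradicts the follow-up rules.** It promises only that collected data will be analysed, which is not literally false. The follow-up rules limit it; they do not conflict with it.
- **That efficacy will be overstated.** This follows only if stoppers gain less than stayers. If they gain equally there is no bias, and if they gain more the change is understated.
- **That the adverse event which makes a patient stop goes unrecorded.** Known events are recorded and withdrawal details go in the case report form, so such an event is likely to be captured. The narrower gap is that active enquiry happens at visits and the final visit of a withdrawn patient is not defined, so events after stopping may be missed.
- **That a patient who stops at week 5 with 15 sessions is a satisfactory completer by the plan's definition.** The protocol applies that count to patients who fall short of 18 over the extended 8 weeks. The example shows only that follow-up depends on time.

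**Conclusion.** The point holds for the secondary efficacy outcomes. As written, the plan yields an estimate for patients who stayed the 6-8 weeks, does not label it so, and has no analysis of how far it may differ from the result for all starters. The documents fix neither the size nor the direction. At an assumed 20% discontinuation the ratio runs from 0.91 to 1.43 over the assumed stopper responses; over the whole grid it runs from 0.83 to 2.50. The listwise-deletion concern is conditional on the usual SPSS default. The primary utility endpoint is not affected. This should be corrected, but it does not undermine the study's main purpose.

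**What to change.** 1. **Follow-up.** In Baseline and follow-up visits, the primary endpoint section, Withdrawal of subjects and Trial exit, separate discontinuing the intervention from withdrawing from the study. This changes data collection only, not who stops HIIT or why. Invite discontinuers who still consent to the scheduled visits, timed from the planned end of their own intervention period (6 weeks, or its extended end, up to 8). Do the questionnaires and AE review where exercise testing is not done. Keep the existing withdrawals for loss of capacity and for exclusion criteria.
2. **Analysis.** State that the efficacy analysis targets all who start HIIT. Replace the general linear model with a linear mixed model using all available visits. State its missing-at-random assumption, and that it does not recover the change of patients with baseline only.
3. **Labelling and sensitivity.** Compare baseline characteristics of leavers and stayers, and label any stayers-only result. For starters without follow-up, add scenarios of no change from baseline and of pre-stated fixed shifts in each outcome's own units, each with a 95% CI. Multiples of the stayers' mean are unsuitable, because they all coincide when that mean is near zero. State that the no-imputation rule covers the main analysis only.
4. **AE period.** Do not shorten it. Keep 30 days after the actual final visit; for patients who stop HIIT early, use the later of that date and 30 days after the planned final visit. Using the planned date for everyone would cut reporting whenever a visit is rearranged. For a 6-week programme the planned last visit is day (6 + 12) × 7 = 126. If it takes place on day 147, reporting now runs to day 177, but would end on day 156.

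**Cost.** A protocol amendment, with REC review if substantial, and probably a revised information sheet. The target already implies up to 50 × 3 + 20 × 2 = 190 follow-up visits of 2-3 hours if all 70 start and nobody stops. At an assumed 20% discontinuation, up to 10 × 3 + 4 × 2 = 38 of these would be for stoppers. Some will decline, so item 3 is needed in any case. If the sponsor keeps the withdrawal rule, the model and sensitivity changes need no extra visits, but the efficacy result must then be labelled stayers-only.
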